8.4. Safety Monitoring

Data and Safety Monitoring Plan

[name] will function as the sponsor of the trial at UAB. The UAB Comprehensive Cancer Center Data and Safety Monitoring Plan (DSMP) instituted by the CTNMO will monitor subjects treated at UAB in the trial. The Clinical Trials Monitoring Committee (CTMC) on a weekly basis will closely monitor adverse reactions observed during treatment. The CTMC is responsible for data and safety monitoring of the trial and adherence to the DSMP. The independent Quality Assurance Committee (QAC) is responsible for oversight of the operation of CTMC, including adherence to the DSMP. Reports from the CTMC are reviewed annually by the QAC.

These committees will monitor safety throughout this study and all studies of Abemaciclib via the following activities:

- Surveillance for SAEs according to regulatory guidelines
- Routine monitoring of non-serious AES as they are recorded in the CRFs and the source documents at study sites

Toxicity information that may affect the treatment of patients on this study will be promptly communicated in writing to all participating Abemaciclib clinical sites, as well as institutions participating in this clinical trial.

9. OTHER ASSESSMENTS

9.1. Other Laboratory Assessments

9.1.1. Tumor Biopsies

Tumor biopsies will be fixed in formalin and embedded in paraffin, and immune cell markers will be assessed by immunohistochemistry and immunofluorescence, focusing on CD8+ T-cells, T regulatory cells, and MDSCs.

9.1.2. Biomarker analysis

The current standard extended-sextant 12 core prostate biopsy technique is essentially a random but systematic sampling in various regions of the prostate gland, serving as a surrogate sampling technique. However, the natural course of most clinically-significant prostate cancer appears to be driven by dominant intra-prostatic lesions (IPL). Advances in multi-parametric prostate MRI (mpMRI) have allowed for identification and radiographic risk stratification of these IPLs, and real-time fusion of mpMRI with trans-rectal ultrasound (TRUS) now allows urologists to perform targeted biopsies of IPLs with optimized detection of clinical significant prostate cancer foci. At UAB, we have analyzed specimens obtained from targeted biopsies from high risk (Gleason score 8 and above) and low risk (Gleason score 6). Using the Nanostring nCounter platform, we were able to find deregulation of various cancer driver pathways (DNA repair, Wnt, Notch, cell cycle, PI3K, and ras) in high risk vs. low risk cancers¹⁴. Furthermore, imaging metrics such as DCE and PiRADS scores also correlated with pathway deregulation. Given these findings, we also propose to use archived tumor tissue from diagnostic biopsy as well as imaging with MRI-US fusion and conducting an optional biopsy at 6 months post-RT. Tumor samples will be assessed for mutations using the Strata Oncology panel and for gene expression analysis using the Nanostring nCounter platform and the PanCancer Pathways panel. Imaging characteristics, such as DCE and PiRADs scores, will be correlated with PSA response and outcomes. Given the emergence of blood-based analysis of biomarkers, we will also collect blood at baseline, pre-radiotherapy (2-3 months of ADT+abemaciclib), 1 and 6 months post-RT to perform molecular analysis to correlate with PSA responses

10. STATISTICS

10.1. Statistical Design/Sample Size

Simon's optimal two-stage design (Simon, 1989) will be used for conducting the trial. The null hypothesis is that the proportion of patients with PSA <0.5 without treatment is 5%, and the alternative hypothesis is that the proportion of patients with PSA <0.5 at 6 weeks into treatment is 30% or higher. The trial is carried out in two stages. In stage I, a total number of 5 patients is accrued. If there are 0 response (PSA < 0.5) among these 5 patients, the study will be early stopped. Otherwise, additional 18 patients will be accrued in stage II, resulting in a total number sample size of 23. If there are 4 or more responses (PSA < 0.5) among these 23 patients, we reject the null hypothesis and claim that the treatment is promising. The design controls the type I error rate at one-sided 0.025 and yields the power of 80%. If we reject the null hypothesis, seven additional patients will be enrolled to explore the association between biomarkers and clinical activities. To account for 10% screen failure, total 33 patients will be recruited to the study.

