definitive RT+ADT. Simon's optimal two-stage design (Simon, 1989) will be used for conducting the trial. The null hypothesis is that the proportion of patients with PSA <0.5 without any treatment is 5%, and the alternative hypothesis is that the proportion of patient with PSA <0.5 at 6 weeks into treatment is 30% or higher. The trial is carried out in two stages. In stage I, a total number of 5 patients is accrued. If there are 0 response (PSA < 0.5) among these 5 patients, the study will be early stopped. Otherwise, additional 18 patients will be accrued in stage II, resulting in a total number sample size of 23. If there are 4 or more responses (PSA < 0.5) among these 23 patients, we reject the null hypothesis and claim that the treatment is promising. The design controls the type I error rate at one-sided 0.025 and yields the power of 80%. If we reject the null hypothesis, seven additional patients will be enrolled to explore the association between biomarkers and clinical activities. Patients receive ADT x 2 years and will start 3 months before RT. Abemaciclib will start with initiation of ADT and pause 2 weeks prior to start of RT. Abemaciclib will resume with the first ADT administration post-radiation, which typically is at 1 month post radiation therapy. Abemaciclib and ADT will continue for a total ADT period of 24 months. Patients will have laboratory evaluation every 2 weeks for the first 2 months and monthly thereafter for the next 2 months. Patients are also seen and evaluated every 4 weeks with laboratory evaluation. Labs may be drawn at outside laboratories at the PI's discretion. For toxicity or adverse event, patients will undergo labs, physical examination and grades of toxicities will be determined using NCI CTCAE version 4.03. Disease response and biochemical failure will be assessed by PSA prior to the start of radiation and every 3 months following the end of radiotherapy and by the investigator (physical exam). The determination of disease progression for the study requires a confirmation of 3 consecutive rises of PSA 3 months apart in the setting of testosterone recovery. Patients will be withdrawn from study for following toxicities,

Toxicity Category	Drug-Related Toxicity/Grade
Hematologic	Grade 4 neutropenia for ≥ 5 days
	Febrile neutropenia: ANC < 1000/mm ³ with a single temperature of $>38.3^{\circ}\text{C}$ (101°F) or a sustained temperature of $\geq 38^{\circ}\text{C}$ (100.4°F) for more than one hour.

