All patients will receive 150 mg Abemaciclib PO BID for 28 days. Patients will receive treatment with Abemaciclib until there is (are) toxicity(ies) or disease progression on treatment or withdrawal from study for any reason. All patients will receive ADT using LHRH analogues every 3 months along with Abemaciclib. There will be no intra patient dose escalation in dosing of Abemaciclib. Patients will take Abemaciclib in clinic on Day 1 of each cycle. They can take the rest of the pills at home. Radiation Therapy will be scheduled at 3 months after C1D1 (Abemaciclib and ADT). Abemaciclib will be stopped 2 weeks before Radiation Therapy and resumed with first dose of ADT after Radiation therapy is completed (usually 1 month after completion of RT). Abemaciclib will continue along with ADT for 24 months (+/- 3 days).

ADT Dose and Administration:

ADT using LHRH analogues will be administered SC beginning on C1D1 and continue during radiation and after radiation for a total of 24 months (+/-3 days) in the absence of toxicity. Dose modification of the ADT is not allowed.

Duration of Treatment:

Patients are eligible for abemaciclib treatment until unacceptable toxicity, or withdrawal of consent, or progression of disease on treatment or maximum of 24 months of ADT on the study. A patient should be withdrawn from study treatment if, in the opinion of the Investigator, it is medically necessary, or if it is the wish of the patient. In addition, patients will be withdrawn from treatment in the case of:

1. A need for surgery, radiation, or for other anticancer therapy not permitted by this protocol
2. Lost to follow-up or noncompliant with the protocol
3. Any Abemaciclib dose delay > 7 days during the first cycle

Parameters to be Assessed:Safety:

Safety assessments will include physical examinations, vital signs, ECOG performance status, laboratory tests (complete blood counts [CBC] and serum chemistry), 12-lead electrocardiograms (ECGs), and additional studies as may be clinically indicated.

Exploratory Biomarkers:

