4. INVESTIGATIONAL PLAN

4.1. Overall Study Design and Plan

4.1.1. Overview

This is a single center, Phase II, single arm, open-label study of Abemaciclib in combination with ADT in patients with localized high-risk or locally advanced prostate cancer who are eligible for definitive RT and ADT.

All patients must sign and date a consent form prior to undertaking any study-related procedures. Prospective patients will be screened to determine if they qualify for the study within 28 days of enrollment. Patients will receive ADT with LHRH analogues every 3 months and will receive Abemaciclib starting on C1D1 at 150 mg PO BID for 28 day cycles Table 3 (see Abemaciclib Administration [Section 6.1.4](#) and ADT Administration). Patients receive ADT x 2 years and will start 3 months before RT. Abemaciclib will start with initiation of ADT and pause 2 weeks prior to start of RT. Abemaciclib will resume with the first ADT administration post-radiation, which typically is at 1 month post radiation therapy. Abemaciclib and ADT will continue for a total ADT period of 24 months (+/- 3 days to allow for holidays and weekends). Patients will have laboratory evaluation every 2 weeks for the first 2 months and monthly thereafter for the next 2 months. Patients are also seen and evaluated every 4 weeks with laboratory evaluation. Labs may be drawn at outside laboratories at the PI's discretion.

Patients will receive study treatment until development of toxicity or disease progression on treatment or any reasons of withdrawal or a maximum of 24 months of therapy with ADT. Adverse events will be graded according to the National Cancer Institute (NCI) Common Terminology Criteria for Adverse Events (CTCAE) Version 4.03.

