All patients will receive Abemaciclib at 150 mg BID PO dose. The trial is carried out in two stages. In stage I, a total number of 5 patients are accrued. If there are 0 response (PSA< 0.5) among these 5 patients, the study will be early stopped. Otherwise, additional 18 patients will be accrued in stage II, resulting in a total number sample size of 23. If there are 4 or more responses (PSA< 0.5) among these 23 patients, we reject the null hypothesis and claim that the treatment is promising. The design controls the type I error rate at one-sided 0.025 and yields the power of 80%. If we reject the null hypothesis, seven additional patients will be enrolled to explore the association between biomarkers and clinical activities. To account for 10% screen failure, total of 33 patients will be recruited to the study.

Table 1: Toxities leading to withdrawal of subjects

Toxicity Category	Drug-Related Toxicity/Grade
Hematologic	Grade 4 neutropenia for ≥ 5 days
	Febrile neutropenia: ANC $< 1000/\text{mm}^3$ with a single temperature of $>38.3^\circ\text{C}$ (101°F) or a sustained temperature of $>38^\circ\text{C}$ (100.4°F) for more than one hour.
	Neutropenic infection: Grade ≥ 3 neutropenia with Grade ≥ 3 infection
	Grade ≥ 4 Anemia
	Grade ≥ 4 thrombocytopenia or Grade ≥ 3 thrombocytopenia with Grade ≥ 3 hemorrhage
Non-hematologic	Grade 2 ($>3.0 \times \text{ULN}$) ALT/AST with total bilirubin $>2 \times \text{ULN}$, in the absence of cholestasis Grade 3 or 4 non-hematologic toxicity with the following exceptions: 
Asymptomatic electrolyte abnormality that resolve within 48 hours.Grade 3 headache lasting <48 hours

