10.2. Data Analysis

Simon's optimal two-stage design (Simon, 1989) will be used for conducting the trial. The null hypothesis is that the proportion of patient with PSA <0.5 without treatment is 5%, and the alternative hypothesis is that the proportion of patient with PSA <0.5 at 6 weeks into treatment is 30% or higher. The trial is carried out in two stages. In stage I, a total number of 5 patients is accrued. If there are 0 response (PSA < 0.5) among these 5 patients, the study will be early stopped. Otherwise, additional 18 patients will be accrued in stage II, resulting in a total number sample size of 23. If there are 4 or more responses (PSA < 0.5) among these 23 patients, we reject the null hypothesis and claim that the treatment is promising. The design controls the type I error rate at one-sided 0.025 and yields the power of 80%. This response rate will be summarized using both a point estimate and its 2-sided 95% confidence limits. If we reject the null hypothesis, seven additional patients will be enrolled to explore the association between biomarkers and clinical activities. Descriptive statistics will be used to summarize patient demographics, baseline characteristics, treatment administration/compliance, efficacy, biomarkers, and archival tumor tissue, safety, and efficacy parameters. Time to PSA failure will be analyzed using the Kaplan-Meier method. The assessment of safety data will be based on the summarization of treatment related AEs, SAEs, AEs leading to discontinuation from study treatment or efficacy follow-up, and clinical laboratory tests. Data will also be displayed graphically, where appropriate.

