10.2.1. Analysis of Primary Objective

For each patient, PSA will be measured on systemic treatment with Abemaciclib and ADT after radiotherapy. The primary endpoint is percentage of patients who achieve the PSA nadir levels of \leq 0.5 ng/ml during their treatment. Simon's optimal two-stage design (Simon, 1989) will be used for conducting the trial. The null hypothesis is that the proportion of patient with PSA <0.5 is 5%, and the alternative hypothesis is that the proportion of patient with PSA <0.5 is 30% or higher. The trial is carried out in two stages. In stage I, a total number of 5 patients is accrued. If there are 0 response (PSA < 0.5) among these 5 patients, the study will be early stopped. Otherwise, additional 18 patients will be accrued in stage II, resulting in a total number sample size of 23. If there are 4 or more responses (PSA < 0.5) among these 23 patients, we reject the null hypothesis and claim that the treatment is promising. The design controls the type I error rate at one-sided 0.025 and yields the power of 80%. This response rate will be summarized using both a point estimate and its 2-sided 95% confidence limits.

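### The 5% null rate refers to untreated men, but every patient receives ADT from day 1, so rejecting it says nothing about what abemaciclib adds

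*Combined protocol and SAP*

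**What the plan says.** The reference for the primary test is worded in three ways:

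- Synopsis, overall design: "The null hypothesis is that the proportion of patients with PSA <0.5 without any treatment is 5" per cent.
- Sections 10.1 and 10.2: "The null hypothesis is that the proportion of patients with PSA <0.5 without treatment is 5" per cent and "The null hypothesis is that the proportion of patient with PSA <0.5 without treatment is 5" per cent.
- Section 10.2.1: "The null hypothesis is that the proportion of patient with PSA <0.5 is 5" per cent, with no reference condition named.

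No section gives a source for the 5%. The alternative is 30% or higher, read at 6 weeks into treatment in the synopsis, 10.1 and 10.2. The rule is to stop at 0 of 5, otherwise go on to 23 patients and reject at 4 or more responses. On rejection, "we reject the null hypothesis and claim that the treatment is promising" (4.1.1 and the statistics sections), and seven more patients are enrolled for biomarker work.

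Section 4.1.1 describes one open-label arm. All patients receive LHRH analogues from C1D1, and "Abemaciclib will start with initiation of ADT and pause 2 weeks prior to start of RT". Radiotherapy (RT) follows about 3 months after C1D1. Section 10.2.1 places the endpoint later than 6 weeks: "PSA will be measured on systemic treatment with Abemaciclib and ADT after radiotherapy". Section 2.4 gives the hypothesis, which is that abemaciclib enhances cytotoxicity in combination with androgen receptor blockade.

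**The concern.** In a single-arm trial the null rate takes the place of the missing control group. To learn what a new drug adds to a background treatment, the null has to be the response rate expected on that background without the drug. Here it is the rate in untreated men. The trial patients differ from that reference by ADT and abemaciclib at 6 weeks, and by RT as well if the endpoint is the on-treatment nadir with PSA measured after RT.

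The documents support the direction of the mismatch. Section 6.2 says that testosterone falls to castrate levels about 2–4 weeks after ADT starts, and the site guideline in Appendix 3 asks for a PSA response check at about 8 weeks of androgen suppression. They do not support a size, because no section gives a PSA response rate on ADT or on ADT plus RT.

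What is at stake is the meaning of a positive result. The reported error rate would be read as protection against a false claim about abemaciclib, which it does not provide.

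**Working it through.** **Inputs (section 10.1).** Stage I: n1 = 5, stop at 0 responses. Stage II: 18 more patients, total 23. Reject at 4 or more. Null 5%, alternative 30%, one-sided alpha 0.025, power 80%.

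**Formula.** For a true response rate p,

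P(reject | p) = Σ over x = 1 to 5 of P[Bin(5, p) = x] × P[Bin(18, p) ≥ 4 − x].

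**Step 1: reproduce the plan's figures.** At p = 0.05:

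| x in stage I | P(x of 5) | P(at least 4 − x of 18) | Product |
|---|---|---|---|
| 1 | 0.2036 | 0.0581 | 0.01184 |
| 2 | 0.0214 | 0.2265 | 0.00485 |
| 3 | 0.0011 | 0.6028 | 0.00068 |
| 4 or 5 | 0.00003 | 1 | 0.00003 |

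The sum is 0.0174, within 0.025. The same formula gives 0.8057 at p = 0.30. A search over designs confirms that 0/5 followed by at least 4/23 is Simon's optimal design for these inputs (expected sample size 9.07 under the null). The arithmetic of the plan is sound.

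**Step 2: how far the error control reaches.** P(reject) rises with p. Solving for p:

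- P(reject) = 0.025 at p = 5.59%
- P(reject) = 0.10 at p = 8.9%
- P(reject) = 0.50 at p = 18.9%

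If abemaciclib adds nothing, the true rate in the trial is the ADT(+RT) rate. A false claim about abemaciclib is therefore held to 0.025 only if that background rate is at most about 5.6%. The threshold is the same whether the endpoint is read at 6 weeks or after RT.

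**Step 3: size over a range.** The background rates below are assumptions. The last column is (1 − p)^5.

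| Assumed ADT(+RT) rate | P(called promising), zero abemaciclib effect | P(stage I stop) |
|---|---|---|
| 5% | 1.7% | 77% |
| 8% | 7.4% | 66% |
| 10% | 13.5% | 59% |
| 15% | 33.6% | 44% |
| 20% | 54.0% | 33% |
| 30% | 80.6% | 17% |
| 50% | 96.9% | 3% |

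At a background of 30%, an inert drug would succeed as often as the planned power. The futility look weakens in parallel.

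**The case against.** The decision rule speaks of the treatment, not of abemaciclib. Section 2.6.1 discusses the benefit of abemaciclib and ADT together, section 3 names safety and tolerability of the combination as the purpose, and section 2.4 calls the trial a pilot. Read that way, 0.025 against a 5% reference is correct for a claim about the regimen. In addition, no document shows that more than 5.6% of these men would reach PSA below 0.5 on ADT alone by 6 weeks. One eligibility route requires a PSA above 20. Finally, the seven-patient expansion is exploratory and can be useful whatever drug produced the responses.

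Much of this stands. The regimen reading is available, the real inflation is unknown, and a rejection driven by the background would not invalidate the biomarker work, although the decision to enrol those patients does depend on the test. None of it removes the point. The plan does not say that the conclusion is confined to the regimen, and next to the hypothesis in 2.4 an unqualified claim of promise will be read as evidence for abemaciclib. Section 10.2.1 drops the words about no treatment, but it does not tie the 5% to ADT(+RT) either. Showing that the background rate is low enough is the plan's task, and it gives no figure.

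**Conclusion.** The concern holds. The 5% is unsourced and, wherever a condition is named, it refers to untreated men. The type I error of 0.0174 (limit 0.025) is valid against that reference only. It covers a claim about abemaciclib only if ADT(+RT) alone yields at most about 5.6%. Beyond that the false-claim probability rises quickly, to 13.5% at a background of 10% and 54.0% at 20%. The threshold is exact for the stated rule. The background rates are assumptions, so the documents establish the gap in the inference but not how large the error would be in practice. This needs correcting before the primary result is interpreted, because it decides what a positive trial means.

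**What to change.** **1. Wording (needed in any case).** In the synopsis and sections 4.1.1, 10.1, 10.2 and 10.2.1, replace the claim of promise with a conclusion of this kind: *the response rate on abemaciclib plus ADT (with RT where applicable) exceeds the 5% reference; the one-sided 0.025 refers to that reference only, and nothing is inferred about the contribution of abemaciclib.* Give the source of the 5%. This costs no patients; the price is a weaker claim.

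**2. Only if an inference about abemaciclib is wanted.** First settle when the endpoint is read (6 weeks, or nadir after RT). Then set the null to a sourced PSA response rate on ADT(+RT) without abemaciclib at that time, and recompute both cut-offs. The RT + ADT historical controls are planned for imaging only. They can serve only if they are confirmed to have PSA at the chosen time, and the site guideline's check at about 8 weeks means that 6-week values may be missing.

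As an illustration, keep 5 and 23 patients and alpha at most 0.025, and take the lowest stage I cut-off that stops at least half of trials under the null:

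| Null rate | Stop at | Reject at | Alpha | Rate detected with 80% power | Power for a 25-point gain |
|---|---|---|---|---|---|
| 10% | 0/5 | ≥6/23 | 0.019 | 35% | 79% |
| 20% | ≤1/5 | ≥9/23 | 0.019 | 52% | 63% |
| 30% | ≤1/5 | ≥12/23 | 0.019 | 60% | 64% |
| 50% | ≤2/5 | ≥17/23 | 0.016 | 80% | 63% |

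These rows show the cost and are not optimised designs. The 25-point gain is the design's own (30% minus 5%). Keeping 80% power for it would take more than 23 patients, plus a control data source and an amended statistics section.

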Given the role of CDK4/6 in tumor resistance to endocrine therapy, in activation of the DNA damage response, and in promoting radiation resistance, we hypothesize that the targeting of CDK4/6 with abemaciclib will enhance the cytotoxicity in combination with blockade of the androgen receptor pathway.

Objectives:

Primary:

- To assess clinical response rates using
 - Proportion of patients with PSA nadir of ≤ 0.5 ng/ml on treatment

Secondary:

- Proportion of patients with PSA declines prior to radiotherapy
- Time to PSA failure
- To study the tolerability and feasibility of combining abemaciclib with androgen deprivation therapy (ADT) for localized high-risk or locally advanced prostate cancer.

Exploratory:

- MRI-US fusion imaging pre-treatment and at 6 months post RT with comparison with historical controls receiving RT + ADT
- Baseline (mandatory) and 6 months (optional) post RT tumor tissue profiling (MRI-US fusion guided) to identify association of molecular profile with PSA decline at 1 year
- Baseline, pre-radiotherapy, and 6 months post-RT blood collection and profiling for molecular analysis

Methodology:

Abemaciclib at 150 mg PO BID, ADT by administering LHRH analogues (goserelin, leuprolide, etc), and radiation therapy in conjunction with ADT

Overall design:

A single institution (UAB) phase II trial is proposed to evaluate the clinical and radiologic response as well as safety and tolerability of abemaciclib in combination with ADT neoadjuvantly and adjuvantly for patients with high-risk localized or locally advanced prostate cancer who will receive

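### The hypotheses are set at week 6 and the primary endpoint is a nadir over up to 24 months; the decision rules name no PSA window, and the 5% null is an unsourced untreated rate

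*Combined protocol and SAP*

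**What the plan says.** **Hypotheses.** Section 10.1: "The null hypothesis is that the proportion of patients with PSA <0.5 without treatment is 5" per cent, and "the alternative hypothesis is that the proportion of patients with PSA <0.5 at 6 weeks into treatment is 30% or higher". The synopsis has the same null ("The null hypothesis is that the proportion of patients with PSA <0.5 without any treatment is 5" per cent). Section 10.2 repeats the alternative: "the proportion of patient with PSA <0.5 at 6 weeks into treatment is 30% or higher".

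**Primary endpoint.** The synopsis and section 3 give "Proportion of patients with PSA nadir of ≤ 0.5 ng/ml on treatment". Treatment runs to a maximum of 24 months of ADT (synopsis, section 4.1.1).

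**Primary analysis.** Section 10.2.1 opens with "PSA will be measured on systemic treatment with Abemaciclib and ADT after radiotherapy". It continues "The primary endpoint is percentage of patients who achieve the PSA nadir levels of" at most 0.5 ng/ml during treatment. It then restates the hypotheses with no time point and no untreated condition: "the alternative hypothesis is that the proportion of patient with PSA <0.5 is 30% or higher".

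**Decision rules.** Wherever they appear (synopsis, 4.1.1, 10.1, 10.2, 10.2.1), the trial stops if none of 5 patients responds and succeeds if at least 4 of 23 respond. A response is given only as PSA below 0.5, with no time attached.

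**Cut-off.** It is at most 0.5 in the endpoint, and strictly below 0.5 in the hypotheses and rules.

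**Source of the rates.** None is given for 5% or 30%. The background (sections 2.1 to 2.4) reports no PSA response rate for untreated patients, ADT alone, ADT plus radiotherapy, or the combination.

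**The concern.** The 0/5 and 4/23 rules are the trial's only formal decision. Two analysts following the text could count different responders in the same patients: one reading PSA at week 6, the other taking the lowest value over two years. At a common cut-off, a nadir window that contains week 6 can only add responders, so that ambiguity favours a positive result.

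The reference rate raises a second problem. The null describes men without treatment, yet ADT starts for everyone on day 1 and radiotherapy follows at about 3 months. Beating an untreated rate does not separate abemaciclib from the therapy given with it.

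Stage II is also worded as conditional on stage I, but nobody can tell when five patients without a response become a final 0/5.

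**Working it through.** **1. The plan's own figure.** Inputs from section 10.1: n1 = 5, stop if 0 respond; n2 = 18; success if at least 4 of 23; p0 = 0.05; p1 = 0.30. With X1 ~ Bin(5, p) and X2 ~ Bin(18, p),

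P(promising) = Σ over x = 1 to 5 of P(X1 = x) · P(X2 ≥ 4 − x).

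At p = 0.05:

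| x | P(X1 = x) | P(X2 ≥ 4 − x) | product |
|---|---|---|---|
| 1 | 0.20363 | 0.05813 | 0.01184 |
| 2 | 0.02143 | 0.22648 | 0.00485 |
| 3 | 0.00113 | 0.60279 | 0.00068 |
| 4 or 5 | 0.00003 | 1 | 0.00003 |

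The sum is 0.0174. The same formula at p = 0.30 gives 0.806. A search over designs with n up to 32 returns this one as the Simon optimum for one-sided 0.025 and 80% power (expected sample size 9.07 under the null). The arithmetic is right.

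**2. The windows side by side.**

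| Place | Window | Cut-off |
|---|---|---|
| Alternative: synopsis, 10.1, 10.2 | week 6 | < 0.5 |
| Alternative: 10.2.1 | none stated | < 0.5 |
| Endpoint: synopsis, 3, 10.2.1 | nadir on treatment, up to 24 months | ≤ 0.5 |
| Measurement sentence: 10.2.1 | after radiotherapy | none stated |
| Both decision rules, everywhere | none stated | < 0.5 |

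Radiotherapy starts about 3 months after day 1, so week 6 lies inside the nadir window but outside the post-radiotherapy one.

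**3. Sensitivity to the reference rate.** Let p be the response rate on background therapy alone in the chosen window. Under no abemaciclib effect, P(promising) is the formula above and P(stop at stage I) = (1 − p)^5. Rates above 5% are assumptions.

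| p | P(promising) | P(stop at stage I) |
|---|---|---|
| 5% | 0.017 | 0.774 |
| 10% | 0.135 | 0.590 |
| 15% | 0.336 | 0.444 |
| 20% | 0.540 | 0.328 |

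Setting P(promising) = 0.025 gives p = 5.6%; setting it to 0.05 gives p = 7.0%.

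**4. When stage I could be read**, counted from the fifth patient's first dose.
- Week-6 window: week 6.
- Post-radiotherapy window: radiotherapy starts at week 12 to 13. Its 28 fractions, at an assumed 5 per week, take 28/5 = 5.6 weeks, so it ends at week 17.6 to 18.6. On Table 2's monthly PSA, add 4.3 weeks: about week 22 to 23. On the synopsis's 3-monthly PSA, add 13 weeks: about week 31 to 32. Appendix 3 likewise says the first PSA should come no sooner than 3 months after radiation.
- Nadir window: a first responder settles the rule at once, but a final 0/5 could take up to 24 months.

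**The case against.** **Error control.** Against its own null of 5% the design holds type I error at 0.0174. A reader might infer that the 0.025 claim is false. It is not: the stated null is controlled, and what is in doubt is what rejecting it means.

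**The reference rate on ADT.** A reader might also infer that it must exceed 5%, because section 6.2 says goserelin brings testosterone into the castrate range in about 2 to 4 weeks. That sentence concerns testosterone only. It gives no proportion with PSA below 0.5, and the documents do not show that the ADT rate is above 5%. The figures of 13%, 34% and 54% are therefore sensitivity values, not estimates for this trial.

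**The stage I window.** It would be too strong to say that the stage I rule uses a window of its own. It states none. In the synopsis, 10.1 and 10.2 it follows the week-6 hypothesis, and week 6 is the natural reading there. In 10.2.1 it follows the nadir endpoint instead.

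**The post-radiotherapy window.** It rests on one sentence and may be a drafting slip, since the next sentence defines a nadir during treatment. The conflict between week 6 and nadir stands without it.

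**Laboratories.** A reader might see a contradiction between drawing laboratory samples outside (Table 2, footnote i) and analysing PSA centrally (section 7.1). Both can be true, and this point does not rely on it.

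**Conclusion.** The endpoint and the hypotheses describe different PSA measures, the cut-offs differ, and the rules that decide the trial name no window or read time. This needs correcting before the stage I read, because choosing the window after seeing PSA values would undermine the stated error rate.

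The numerical design is sound for 5% against 30%. The weakness lies in interpretation: rejecting an unsourced, untreated 5% does not establish that abemaciclib adds to ADT. The margin is narrow. A background-therapy rate above about 5.6% in the chosen window takes the chance of a false *promising* conclusion about abemaciclib past 0.025. How far past cannot be said from the documents, which give no such rate.

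**What to change.** Before stage I is read:

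- Choose one window and one cut-off (the sponsor's choice) and use them for the endpoint, the hypotheses and both rules in the synopsis and sections 3, 4.1.1, 10.1, 10.2 and 10.2.1. Report the other PSA measure as secondary.
- Replace the untreated null with the rate on the trial's background therapy in that window (ADT, plus radiotherapy if the window includes it), and cite its source. Give the source of the alternative too.
- If that rate is not 5%, restate the error rates or recompute the cut-off within the planned patients. For example, at an assumed 10%, keeping 5 + 18 patients and the 0/5 rule, success at 6 or more of 23 gives type I error 0.019 and power 79% against 35%. Success at 5 or more would give 0.056.
- State when the five stage I patients are read, that a responder in the chosen window satisfies the rule as soon as seen, and that stage II accrual waits for this.
- If week 6 is chosen, name it in the Table 2 PSA row; at present it can only be derived from footnote i. If a nadir or post-radiotherapy window is chosen, reconcile the PSA timing in Table 2, the synopsis and Appendix 3.

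**Cost.** If 5% can be supported on background therapy, this is a wording change and one PSA measure becomes secondary. If not, power may fall slightly (79% in the example, against 80.6% now). The example needs no patients beyond the 23.
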